7.5. Monitoring and Management of Potential Hepatic Injury and/or Disease Progression

Given the chronic nature of PBC, it is important to monitor for potential hepatic injury, disease progression and/or hepatic decompensation. Child-Pugh and MELD scores will be reviewed at each visit where labs are drawn ([Table 1](#)). Child Pugh Scores should only be applied in patients who have evidence of cirrhosis at screening or demonstrate evidence of cirrhosis at screening or progression to cirrhosis during the study based on criteria presented in [Section 7.5.4](#). In addition, adverse events, signs and symptoms of potential hepatic injury or decompensation, and laboratory values will also be reviewed at regular intervals as described in [Section 7.1.1](#). Based on the assessments of signs and symptoms of hepatic injury and liver biochemistry, the investigational product may be interrupted or discontinued per criteria discussed in [Section 7.5.2](#) and [Section 7.5.3](#), and close monitoring procedures will be implemented ([Section 7.7](#)).

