Baseline \leq ULN and 1.5 mg/dL increase from baseline Baseline $>$ ULN and 1.0 mg/dL increase from baseline	If values continue to increase relative to the baseline value, interrupt IP.	If laboratory values do not normalize, IP should not be restarted.
INR^b		
$>$ 0.3unit increase from baseline	Closely monitor until normalization or stabilization. If values continue to increase relative to the baseline value, interrupt IP.	The subject may be rechallenged after a minimum of 30 days if fully resolved OR stable and approved by the Medical Monitor and Investigator. If laboratory values do not normalize, IP should not be restarted.
\geq 2.0 unless due to vitamin K deficiency	Discontinue IP permanently	Continue to return for scheduled study visits for safety follow up. Monitor closely for clinical outcomes per protocol.
C. Laboratory Criteria for Monitoring Potential Hepatic Decompensation in the Presence of Clinical Symptoms		
Total bilirubin thresholds defined in Part B OR an INR increase from baseline of \geq 1.5 are observed in the presence of clinical symptoms of cholestatic hepatitis or hepatic encephalopathy ^c	Discontinue IP permanently	Continue to return for scheduled study visits for safety follow up. Monitor closely for clinical outcomes per protocol.

IP = investigational product

^a Sodium will be measured as an assessment of liver failure (hyponatremia).

^b Does not apply in subjects on anti-coagulants.

^c Symptoms of cholestatic hepatitis includes dark urine and jaundice. Symptoms of hepatic encephalopathy may include lack of awareness, shortened attention span, lethargy, gross disorientation, or coma (unresponsive to verbal or noxious stimuli)

It should be noted that it is difficult to recognize every potential marker of hepatic or renal deterioration. There is no substitute for good medical judgment. Investigators will be reminded to be cautious and mindful in their evaluation of subjects' symptoms, signs, and laboratory results. However, for example, a single abnormal laboratory analyte result may be artefactual; accordingly, Investigators will be allowed to implement an alternate follow-up procedure if

considered appropriate based on their medical judgement but only after documented agreement with the Sponsor's Medical Monitor.

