
 • Liver failure defined as worsening synthetic function that is persistently worse relative to baseline and/or progressive over time (see Table 4, Part B)^a • Variceal bleeding or recurrent variceal bleeding^b documented by endoscopy or accompanied by anemia or melena with a hemoglobin drop of ≥ 2 g/dL • Ascites^c including: 
 ○ Worsening – requires increase in drug therapy or surgical intervention (paracentesis or shunt procedure) ○ Refractory ascites – unresponsive to medication; patient not candidate for transjugular intrahepatic portosystemic shunt (TIPS) or shunt; requires large volume paracentesis ○ Hyponatremia (≤ 125 mEq/L) secondary to ascites • Spontaneous Bacterial Peritonitis • Hepatic Encephalopathy, Grade ≥ 2 • Any liver-related event requiring hospitalization and treatment (except multi-organ failure) • Hepatorenal syndrome Type 1 or Type 2 and acute kidney injury, hepatopulmonary syndrome, or portopulmonary syndrome 	
Closely monitor until normalization or stabilization.
 
The patient may be rechallenged after a minimum of 30 days if fully resolved OR stable and approved by the Medical Monitor and Investigator
 
IP should be re-initiated at a lower dose (or lower dose frequency) and titrated per Investigator discretion.

^a Patients experiencing INR ≥ 2.0 unless due to vitamin K deficiency should be discontinued from IP permanently without rechallenge and should to return for scheduled study visits for safety follow up.

^b Endoscopic confirmation of gastric or duodenal varices without evidence of bleeding should be closely monitored; investigational product may be interrupted at Investigator discretion.

^c New onset ascites requiring treatment should be closely monitored; investigational product may be interrupted at Investigator discretion.

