7.6. Dose Adjustment, Interruption, and Withdrawal from Investigational Product or Study

Investigational product may be temporarily decreased (eg, from 10 mg twice weekly to 5 mg twice weekly, or from 5 mg twice weekly to 5 mg once weekly) or temporarily or permanently stopped based on safety and/or tolerability concerns. Investigational product may be resumed at the maintenance dose upon resolution of gastroenteritis or worsening renal function or dehydration if there is no evidence of liver injury. For rechallenge, following all other dose interruptions (see Table 7), investigational product should be initiated at a lower dose and subjects monitored more frequently with up-titration considered based on tolerability.

Adjustments, interruptions, discontinuation, and any rechallenge of investigational product should be implemented per the criteria outlined in Table 7. Subjects who discontinue investigational product are expected to continue in the study (and follow the regular visit schedule) until the end of the study, and the study will terminate at the time when the needed number of adjudicated events has accrued. If a subject reaches an outcome event, he or she should continue the regular visit schedule and continue taking investigational product as long as the subject has not met any of the criteria for mandatory interruption of investigational product outlined in Table 7, and the Investigator assesses it as safe to continue. In general, subjects should be strongly encouraged to both stay on investigational product and remain in the study until study termination. If a subject discontinues investigational product and cannot continue to attend regularly scheduled study visits, the subject should be strongly encouraged to participate in study follow-up via phone calls or electronic medical record review as described in [Section 7.9](#).

Table 7: Criteria for Dose Adjustment, Interruption, Discontinuation and Rechallenge

DOSE ADJUSTMENT		
Criteria	Action Taken with IP	Adjustment
Progress to cirrhosis and have CP A cirrhosis (CP score <7)	Adjust to a maximum daily dose of 10 mg (or equivalent placebo) in a blinded fashion	Not applicable. Remain at maximum daily dose of 10 mg (or equivalent placebo) for remainder of study.

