Progress to CP B or C cirrhosis (CP score ≥7)	Adjust IP dose to 5 mg once weekly, then titrate to a maximum 10 mg twice weekly (at least 3 days apart).	After a minimum of 3 months, if at a lower dose, subjects may titrate to a maximum IP dose of 10 mg twice weekly per Investigator discretion.
New onset Severe Pruritus	Drug holiday or less frequent dosing	Return to original dose regimen if tolerated
DOSE INTERRUPTION		
Criteria	Action Taken with IP^a	Rechallenge^b
If liver biochemistries indicative of suspected hepatic injury are identified as exceeding upper threshold criteria and require immediate interruption (see Part A of Table 4) ^c	Interrupt immediately upon initial observation	Patient may be rechallenged after a minimum of 30 days if fully resolved OR stable and approved by the Medical Monitor and Investigator.

Table 7: Criteria for Dose Adjustment, Interruption, Discontinuation and Rechallenge (Continued)

Other liver biochemistries indicative of suspected hepatic injury are outside upper threshold criteria upon repeat testing as defined in Part A of Table 4 ^d	Interrupt after confirmation by repeat testing	
Liver biochemistries indicative of potential hepatic decompensation in the absence of symptoms (see Part B of Table 4) ^e	Closely monitor until normalization or stabilization. If values continue to increase relative to the baseline value, interrupt	
Clinical events indicative of hepatic decompensation (see Part B of Table 5)	Closely monitor until normalization	The subject may be rechallenged after a minimum of 30 days if fully resolved OR stable and approved by the Medical Monitor and Investigator. IP should be re-initiated at a lower dose (or lower dose frequency) and titrated per Investigator discretion.
Gastroenteritis (established severe abdominal pain, vomiting, diarrhea for more than 4 days)	Interrupt	If no evidence of liver injury is detected, IP may be restarted at the same dose after resolution of intercurrent illness.
Evidence of worsening of renal function or dehydration	Interrupt	
Pregnancy	Interrupt	Patient should continue with the study visit schedule. The subject may re-start IP when she is no longer pregnant or breastfeeding (if applicable) at the discretion of the Investigator and after discussion with the Medical Monitor
DOSE DISCONTINUATION		
Criteria	Action Taken with IP	Rechallenge

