If INR increases ≥ 2.0 in absence of clinical symptoms criteria (unless due to vitamin K deficiency)	Discontinue / No Rechallenge	Discontinue IP permanently and continue to return for scheduled study visits for safety follow up. Monitor closely for clinical outcomes per protocol. Continue to return for scheduled study visits for safety follow up. Monitor closely for clinical outcomes according to protocol assessments.
If total bilirubin, thresholds (Part B of Table 4) are observed in the presence of clinical symptoms of cholestatic hepatitis or hepatic encephalopathy ^f		
Multi-Organ failure requiring hospitalization		
Liver transplantation		

Fully resolved = Return to baseline levels or return to within normal limits (WNL). IP = investigational product

^a If subject is unable to be evaluated promptly, study drug must be immediately interrupted.

^b Requires complete documentation of complete resolution or normal/baseline results based on laboratory parameters and symptoms.

^c Total bilirubin baseline \leq ULN and Postbaseline $\geq 3x$ baseline, Baseline $>$ ULN and Postbaseline $\geq 2x$ Baseline, ALT or AST $> 3x$ baseline (and $>$ ULN)

^d ALT or AST $\geq 2x$ baseline, albumin < 3.2 g/L or electrolytes (sodium < 130 mEq/L).

^e Conjugated bilirubin > 0.5 mg/dL increase from baseline; Total bilirubin Baseline \leq ULN and 1.5 mg/dL increase from baseline OR Baseline $>$ ULN and 1.0 mg/dL increase from baseline; INR > 0.3 increase from baseline

^f If INR increases ≥ 2.0 in the absence of clinical symptoms or if conjugated bilirubin or total bilirubin, thresholds OR an INR increase from baseline of ≥ 1.5 are observed in the presence of clinical symptoms of cholestatic hepatitis or hepatic encephalopathy.

^g Multi organ failure including hepatorenal syndrome Type 1 or Type 2 and acute kidney injury, hepatopulmonary syndrome, or portopulmonary syndrome.

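### Table 4 exempts anticoagulated subjects from the permanent stop at INR ≥2.0 without symptoms, but Tables 5 and 7 restate that stop without the exemption

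*Protocol*

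**What the plan says.** The rule for a raised INR without symptoms appears in three tables of the current protocol (Version 6).

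- **Section 7.5.2, Table 4, Part B.** Two INR rows stand under one heading. A rise of more than 0.3 from baseline calls for close monitoring, then interruption if values keep rising. INR ≥2.0 calls for permanent discontinuation unless vitamin K deficiency explains it. The heading carries footnote b: "Does not apply in subjects on anti-coagulants".
- **Section 7.5.3, Table 5, footnote a.** Subjects with INR ≥2.0 "unless due to vitamin K deficiency should be discontinued from IP permanently without rechallenge". Anticoagulants are not mentioned.
- **Section 7.6, Table 7, Dose Discontinuation.** The trigger is an INR increase of ≥2.0 "in absence of clinical symptoms criteria (unless due to vitamin K deficiency"), and the action is discontinuation with no rechallenge. Footnote f repeats the trigger in its first clause with no exception at all.

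Two passages say which text sites should act on. Section 7.5 says that "the investigational product may be interrupted or discontinued per criteria discussed in" Sections 7.5.2 and 7.5.3, which hold Tables 4 and 5. Section 7.6 says: "Adjustments, interruptions, discontinuation, and any rechallenge of investigational product should be implemented per the criteria outlined in Table 7".

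Section 9.2 tells investigators to monitor INR and adjust warfarin to its target range. Section 9.2.1 prohibits only commercial OCA. Warfarin is therefore permitted.

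**The concern.** The three tables state what is evidently one criterion: same threshold figure, same permanent action, and in the Table 4 and Table 7 rows the same symptom-free setting and vitamin K exception. Only Table 4 takes anticoagulated subjects out of it. The table that Section 7.6 names for carrying out the stop lacks the exemption.

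At stake is assigned treatment for the subjects concerned. The stop is permanent, so a site that follows Table 7 cannot reverse it once Table 4 is noticed. Two sites with identical facts can act differently and each be following the protocol.

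**Working it through.** The plan states no figure to reproduce. The check sets the tables side by side and applies them to one case.

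**Case:** no clinical symptoms, on warfarin, INR 2.0, no other criterion met.

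| Source | Exceptions stated | INR-based action |
|---|---|---|
| Table 4 Part B, rise >0.3 | anticoagulants (footnote b) | none |
| Table 4 Part B, INR ≥2.0 | vitamin K deficiency; anticoagulants (footnote b) | none |
| Table 5 footnote a | vitamin K deficiency only | permanent stop, no rechallenge |
| Table 7 discontinuation row, read as a level | vitamin K deficiency only | permanent stop, no rechallenge |
| Table 7 footnote f, first clause, read as a level | none | permanent stop |

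Table 4 applies 0 of its 2 Part B INR rows. Tables 5 and 7 order an irreversible stop.

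**Can a reader get from Table 7 to the exemption?** From one row, yes. The interruption row reads "Liver biochemistries indicative of potential hepatic decompensation in the absence of symptoms (see Part B of Table 4"), so a reader sent to Part B meets footnote b. That covers the smaller threshold, which Table 7 footnote e gives as INR > "0.3 increase from baseline". The INR discontinuation row has no such pointer. It gives its own threshold and its own exception and reads as complete. Table 5 footnote a hangs on a liver-failure entry that points to Table 4 Part B, but it too states its own rule and its own single exception.

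**Level or rise?** Table 7 speaks of INR increasing by or to 2.0; Tables 4 and 5 give a level. If Table 7 means a rise, the trigger is baseline + 2.0:

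- assumed baseline 1.0: 1.0 + 2.0 = 3.0
- assumed baseline 2.5: 2.5 + 2.0 = 4.5

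That reading moves the point at which Table 7 acts. It does not supply the exemption, and Table 5 footnote a still acts at a level of 2.0.

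**Rule with symptoms, for contrast.** The part of Table 4 titled "C. Laboratory Criteria for Monitoring Potential Hepatic Decompensation in the Presence of Clinical Symptoms" orders a permanent stop at an INR increase of ≥1.5 from baseline. It carries no anticoagulant exemption, and the second part of Table 7 footnote f gives the same rule. With the same assumed baselines, both tables act at 1.0 + 1.5 = 2.5 and 2.5 + 1.5 = 4.0. There is no conflict there.

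**The case against.** The best defence is that the intent can be recovered. Section 7.5 makes Table 4 operative for discontinuation, and Table 4 carries the more specific text. Section 7.5.4.1 also discounts an INR elevation caused by antithrombotic agents when cirrhosis is assessed. Section 7.5.2 lets an investigator use an alternate follow-up procedure with documented Medical Monitor agreement. All of this supports the view that the omission was unintended, but none of it says which table prevails. The Medical Monitor route works case by case, and a site following Table 7 has no prompt to use it.

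Reach may also be limited. Section 8.3 excludes subjects with a MELD score above 12. MELD is calculated from chemistry and coagulation results, so screening may work against enrolling subjects whose INR is already high. That stands as a direction only, since the documents give no MELD formula. It does not cover subjects who start an anticoagulant during a study of about 10 years.

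Two points against a stronger reading stand in full. A reader might infer that Table 7 stops these subjects for a purely non-hepatic reason. The documents do not support that: neither table establishes cause, and in a cirrhotic subject on warfarin a raised INR may be partly hepatic. A reader might also want the exemption written as a causal exception, for INR elevations due to anticoagulant use. That would not match footnote b, which is categorical. A subject on warfarin whose INR was judged hepatic would remain exempt under Table 4 but be stopped under Tables 5 and 7.

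**Conclusion.** The inconsistency is real. An asymptomatic subject on permitted warfarin who reaches the threshold has no INR-based stop under Table 4 and is permanently stopped without rechallenge under Table 7 and Table 5 footnote a. It should be corrected, as an internal inconsistency of minor to moderate severity.

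The conclusion rests on two readings: that footnote b, placed on the INR heading, governs both rows beneath it, and that the Table 7 row is the same criterion as Table 4's INR ≥2.0 row despite the word about increasing. The missing exemption does not depend on the second reading; only the INR at which Table 7 acts does.

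The number of subjects affected is unknown, and none is claimed. A reader might infer damage to the primary analysis. The documents do not support that inference: subjects who stop product are to remain in follow-up and stay in the ITT population under their randomized treatment. The demonstrated consequence is avoidable ambiguity about an irreversible treatment decision for individual subjects.

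**What to change.** Use footnote b's categorical wording, "Does not apply in subjects on anti-coagulants", or a cross-reference to Table 4 footnote b, in three places:

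1. the Table 7 INR discontinuation row;
2. the first clause of Table 7 footnote f;
3. Table 5 footnote a.

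Write the Table 7 threshold, in the row and in that clause, as INR ≥2.0 to match Tables 4 and 5. For consistency, the same wording may be added to the INR >0.3 part of Table 7 footnote e; this is optional, because its row already points to Table 4 Part B.

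Leave unchanged the rule for an INR increase of ≥1.5 with symptoms (Table 4 Part C and the second part of footnote f) and all bilirubin and clinical criteria, so these subjects remain under hepatic monitoring.

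The cost is a few words in one table row and two footnotes, or three with the optional change. No new data are needed, because Section 9.2 already requires concomitant medications to be recorded.

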7.7. Close Observation

If investigational product is interrupted or discontinued as described in [Section 7.6](#), subjects should be closely monitored (contacted by the site a minimum of every 2 weeks and scheduled visits every 6 weeks; if returning to the site for a scheduled visit is not feasible, use of a local lab may be permissible at the Investigator's discretion). At a minimum, the following assessments should be conducted at each study visit:

- Physical exam and thorough review of subject reported signs and symptoms,
- Liver biochemistry (including ALP, ALT, AST, GGT, total and conjugated bilirubin, creatinine, and albumin), prothrombin time (PT)/INR, serum electrolytes, and assessment of Child Pugh (only if the subject is at the study site) and MELD scores.

In addition, a trough pharmacokinetic sample for assessment of OCA serum drug levels and its major metabolites should be obtained in any subject who develops an AE that is indicative of or consistent with hepatic injury or decompensation.

The following additional monitoring procedures should be performed for events of potential hepatic injury (per FDA Guidance for Industry on Drug Induced Liver Injury) or suspected hepatic decompensation based on criteria described in [Section 7.5.1](#), [Section 7.5.2](#), and [Section 7.5.3](#). These cases need to be discussed with the Sponsor's medical monitor:

- Repeating liver enzyme and serum bilirubin tests as described in [Section 7.5.2](#). Frequency of retesting can decrease to once a week or less if abnormalities stabilize or the study drug has been discontinued and the subject is asymptomatic, as clinically indicated.
- Obtaining a more detailed history of symptoms and prior or concurrent diseases.
- Obtaining a history of concomitant drug use (including nonprescription medications and herbal and dietary supplement preparations), alcohol use, recreational drug use, and special diets is important. Concomitant drugs with potential hepatotoxicity should be recorded and discontinued unless alternative therapies are not available. In the case of concomitant drugs potentially hepatotoxic, continued use of investigational product should be discussed with the Sponsor's medical monitor. The subject may be discontinued from investigational product, if clinically appropriate.
- Obtaining a history of exposure to environmental chemical agents or herbal supplements which may be associated with liver toxicity.
- Ruling out acute viral hepatitis types A, B, C, D (in those thought to have acute HBV infection), and E; autoimmune or alcoholic hepatitis; Wilson's disease, hypoxic/ischemic hepatopathy; and biliary tract disease.
- Investigators should consider testing for Hepatitis E virus (HEV) when assessing for hepatic decompensation as infection with HEV in patients with chronic liver diseases

such as PBC may rapidly worsen with signs and symptoms similar to drug induce liver injury ([Kumar 2013](#))

- Obtaining additional tests to evaluate liver function, as appropriate (e.g., INR, direct bilirubin).
- Seeking hepatology consultation, if the Investigator is not a hepatologist

7.8. Criteria for Study Termination

The Sponsor reserves the right to terminate the study at any time. It is normal procedure to review the emerging clinical and safety data. As a result of such a review or a recommendation by the DMC, it may be necessary to stop the study before all events have been accrued, and when subjects are still active on the study. In addition, the Sponsor may terminate the study at an investigational site at any time (eg, poorly performing sites, as determined by the number of subjects enrolled or the quality of the study data).

The Investigator and/or Sponsor (or designee) must notify the Institutional Review Board/Independent Ethics Committee (IRB/IEC) of discontinuation of a site or the study and the reason for doing so. Investigators will be informed by the Sponsor as to when the final study visit is to be completed, and should then schedule all subjects for the End of Study Visit. The window of time for scheduling the visit will be based on a final projection of when the requisite 127 adjudicated events will have been accrued.

